There has been no additional adaptation of the Kitbag itself from the school setting but the support is tailored to the social work setting, focusing on the relationship-based and reflective practice skills of the social workers and their role in leading the shift in practice within their teams.

As mentioned above, we expect that the version of the programme trialled will involve considerably more use of the Kitbag Online than in non-Covid-19 times. We attempt to address the generalisability of the findings in the implementation and process evaluation (please see below).

Logic model

* indicates outcomes that will be measured.

Impact Evaluation

Research questions

Primary research questions

Child outcomes:

- Primary outcome 1: What is the impact of the “Putting the Kitbags to work” programme on the number of **escalations and de-escalations** of eligible children supported by social workers? The comparison is between eligible children supported by social workers in teams randomly allocated to the intervention arm compared with eligible children supported by social workers in teams randomly allocated to the control arm within the intervention period.
- Secondary outcome 1: What is the impact of the “Putting the Kitbags to work” programme on the **behaviour** of eligible children supported by social workers? The comparison is between eligible children supported by social workers in teams randomly allocated to the intervention arm compared with eligible children supported by social workers in teams randomly allocated to the control arm. The outcome will be measured by the total difficulties score of the Strengths and Difficulties Questionnaire. The population will be restricted to children who’ve been looked after continuously for 12 months or more whose SDQ has been assessed from T4 - T12.

Social worker outcomes:

[figure not shown]
- Secondary outcome 2: What is the impact of the “Putting the Kitbags to work” programme on the **self-efficacy** (as measured by the competency subscale of the Work-Related Basic Needs Satisfaction scale) of social workers and family support workers in teams randomly allocated to the intervention arm compared with social workers and family support workers in teams randomly allocated to the control arm? The outcome will be measured at month 6 and month 13 after intervention began.

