Since the intervention is allocated by team, we define eligibility criteria for teams: statutory teams who we would typically expect to conduct longer term (4+ months) work with children and young people to allow for the minimum number of sessions with a Kitbag. This includes safeguarding teams who work with child and young people who are subject to a child in need (CIN) plan or a child protection plan (CPP), teams that work with children who are looked after (CLA) or teams who work with children with disabilities. Please see Table 1 for the number of eligible teams per local authority. As different local authorities have slightly different names for each team, we've included the type of team in brackets. The teams we have determined are not eligible to participate therefore, are MASH / front door, assessment, early help, youth justice and leaving care teams as they do less of the longer term direct work. Please see Table 2 for the number of social workers, family support workers and foster carers.

Table 1: Eligible teams within each local authority

Local authority	Eligible teams
Bexley	Family support and child protection teams (North, East, Central and South, South West) (4 CIN / CPP teams) Looked After Children team (1, 2, 3) (3 CLA teams) Children with Disabilities team (1, 2) (2 Children with disabilities teams) Total: 9 eligible teams
Haringey	Children in Care team (1, 2) (2 CLA team) Disabled Children's team (1, 2) (2 Children with disabilities teams) Safeguarding and Support team (1-6) (6 CIN / CPP teams) No Recourse to Public Funds team (1 CIN / CPP teams) Total: 11 eligible teams
Oxfordshire	Children's Disability Teams (North, South, City) (3 Children with disabilities teams) Family Solutions Plus Teams (North 1-6, Central 1-5, South 1-6) (17 CIN / CPP teams) Rosehill Statutory Teams (1, 2) (2 CIN / CPP teams) Unaccompanied Children (1 CLA team) Children in Care (North 1, North 2, South 1, South 2, Central 1a, Central 1b, Central 2) (7 CLA teams) Total: 30 eligible teams
Warwickshire	Safeguarding and support (Bedworth and North Warwickshire, Nuneaton, Rugby, Stratford, Warwick) (5 CIN / CPP teams) Children in Care aged 14-18 (1 CLA teams) Strengthening Families (1 CIN / CPP team) Children with Disabilities (safeguarding and support hub, children in need hub, strengthening families hub) (3 Children with disabilities teams) Total: 10 eligible teams
Total	60

Social workers and family support workers

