If the sample is imbalanced with respect to team type (CIN / CP, CLA, children with disabilities) within the local authority, we will re-randomise (setting a new seed). We take imbalance to be the proportion of teams of that type within the local authority assigned to the intervention to be greater than 0.75 or less than 0.25 (i.e. $\frac{3}{4}$ or $\frac{1}{4}$ teams) except where there is only one team of that type in the local authority.

We will also report the mean proportion of social workers to family support workers, and the mean proportion of permanent staff to agency staff, by treatment allocation but will not re-randomise if there is imbalance in treatment allocation on these variables. With a relatively small number of teams to allocate, we have decided to prioritise team type (within the local authority) to enable us to compare the impact of the programme on these subgroups.

Data collection

We have several data collection methods:

Impact evaluation

- Children and young people:
 - administrative data to measure children's social care involvement
- Social workers:
 - online survey to measure self-efficacy, stress
 - administrative data to measure sickness absence
- Foster/kinship carers:
 - online survey to measure self-efficacy

⁷ Due to a delay of the required data from Oxfordshire County Council, the randomisation was conducted for the three other local authorities first, and the teams from Oxfordshire County Council were allocated separately.

Sample size / MDES calculations

		MDES (Proportion of a Standard Deviation)
MDES		0.127
Proportion of variance in child's outcome explained by:	Child covariates (including baseline measure)	0.8
	Social Worker team covariates	0.1 (3 covariates)
Intraclass correlations (ICCs)	Team	0.03
Alpha		0.05
Power		0.8
One-sided or two-sided?		Two-sided
Level of intervention clustering		Social worker team
Average cluster size		150 children in each team
Sample Size (children)	Intervention	4500
	Control	4500
	Total	9000
Sample Size (teams)	Intervention	30 (15 per local authority)
	Control	30 (15 per local authority)
	Total	60

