As represented in the logic model, one of the hypothesised mechanisms is carer self-efficacy. We measure parental / carer self-efficacy - “the parents’ beliefs about their effectiveness in overcoming or solving specific parenting problems” - using the parental self-efficacy subscale of the “Me as a parent” scale. The subscale consists of 4 questions and has been validated for parents of children aged 6 months to 15 years old. The subscale has good internal reliability (Cronbach’s alpha of .75), good test-retest reliability (.73), and good convergent validity (Pearson $r = .63$, $p.001$ between the 4 items of the MaaP self-efficacy subscale and the 8 items of the efficacy subscale of the 17-item Parent Sense of Competence scale²⁰). The questions will be adapted to account for those in non-parental caring roles. The population will be restricted to local authority employed foster carers only as these are the foster carers whom we will be able to access.

Analysis plan

Primary and Secondary Analysis

Primary analysis estimates the impact of the programme on our primary outcomes, whilst secondary analysis estimates the impact of the programme on our secondary outcomes. As the approach is the same, we outline it jointly below.

Models

The dependent variables are continuous and we will use an OLS regression. The regression coefficient on the treatment variable is interpreted as the impact of the intervention on the dependent variable (in the units described in the “Outcomes” section). Please see the “Outcomes” section for the expected direction of the impact.

¹⁸ Yankelovich, & Broadfoot, & Gillespie, Michael & Guidroz, Ashley. (2012). The Stress in General Scale Revisited: A One-factor Structure.. *Stress and Health*. 28. 137-148. The items (p.144) are Demanding, Pressured, Calm (R), Many things stressful, Nerve-wracking, Hassled, More stressful than I’d like, Overwhelming where (R) means reverse coded.

¹⁹ The Scale is usually calculated as the sum; however, we use the mean to allow for non-response.

²⁰ Hamilton, V. Matthews, J. & Crawford, S. (2014). Development and Preliminary Validation of a Parenting Self-Regulation Scale: “Me as a Parent”. *Journal of Child and Family Studies*. 24. 10.1007/s10826-014-0089-z.

Independent variable of interest: treatment

For the outcomes of social workers, family support workers and foster carers, treatment is coded as a binary variable where treatment = 1 if:

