Children are clustered into sibling groups, households (e.g. with other children in foster care) and caseloads (i.e. a group of children have the same social worker) and social worker teams. Because of this clustering, observations within one group (sibling group, household etc) may be more similar with each other on various characteristics compared with observations in other groups violating the assumption of independence. When data is structured in this way, the estimation of the treatment effect remains unbiased but the standard errors may be misspecified, leading to problems with inference. To correct for this, standard errors will be clustered at the level of randomisation, the social worker team level, in line with WWCS statistical guidance. This also accounts for correlations between observations at lower levels of nesting.

Handling non-compliance

If CYP are transferred to another team (e.g. due to a change of status), it is possible that the team to which they are transferred was ineligible for participating in the programme or had a different intervention / comparator group allocation. If a social worker or family support worker changes teams, it is possible that their new team had a different intervention/ comparator allocation. For all our analysis, we will conduct intention to treat analysis where a CYP is considered as treated if they are / were supported by a social worker who is a member of an intervention team at the point they entered the sample (either at randomisation or when their case started), irrespective of their use of Kitbag.

Multiple Comparison Adjustments

We will adjust for multiple comparisons within the secondary outcomes using Hochberg's step-up procedure, as per WWCS statistical guidance.

Regression specification

For social workers, family support workers and foster carer outcomes:

$$Y_{ict13} = \beta_0 + \beta_1 D_c + \beta_{2:4} A_c' + \beta_5 Y_{ict0} + \beta_{6:k+6} X_i' + \beta_{k+6:k+11} M_c' + \epsilon_c$$

Where:

- Y_{ict13} is the dependent variable for individual i , team c at the end of the trial, $t13$. β_0 is the intercept
- D_c is the treatment variable
- A_c is a vector of the local authority fixed effects
- Y_{ict0} is the "pre" outcome of individual i in team c , at their "pre" data collection point, $t0$
- X_i' is an $N \times k$ matrix of characteristics of individual i
- M_c' is an $N \times 5$ matrix of characteristics of team c
- ϵ_c is the error term clustered at the team level c

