Focus groups	T10-T12	
We will send information about the focus groups to the practitioners via the Kitbag super lead and then purposively sample aiming for a heterogenous sample of practitioners from different team types and of different roles.
 
For the focus group discussions for the super leads, all will be invited to attend.

Interviews (n=16)	T10-T12	
Children: Practitioners who attend the focus group discussion will be asked to identify children on their caseload who may be open to participating.
 
Foster carers: the Kitbag leads in the fostering teams will be asked to send information about the interviews to the foster carers. We

		will purposively sample aiming for a heterogenous sample of foster carers of children of different ages.
Survey (assume 10% response rate)	T1 T13	A survey will be shared with all staff (i.e. no sampling) across intervention and comparator teams: 
 • Social workers and family support workers (includes Kitbag Leads) • Inhouse foster carers (the survey will be adapted slightly for this group) • Team Managers
Observations of workshops (n=4)	T3-T4	A researcher or research assistant will observe at least one workshop per local authority.

Analysis

Qualitative data preparation and analysis of interview and observational data

Interviews will be recorded, transcribed and pseudonymised prior to analysis. Qualitative analysis of interview and observational data will use NVivo software and follow a thematic analysis approach. This will involve data familiarisation, checking accuracy of transcription, labelling the data with descriptive codes and developing themes which describe patterns across the data to answer the pre-specified research questions. Analysis will look for patterns, consistencies and inconsistencies across different informants and time points that might be informative for the research questions.

The following steps will be taken to ensure rigor in the analysis and reporting of qualitative data:

- Confidence that the findings are an accurate reflection of participant experience will be ensured through presentation of examples of participant responses using quotes, and triangulation between different informants and data collection methods.
- The degree to which findings are transferable to other contexts will be considered through detailed description of contextual factors, and collection of data from a range of informants to gather a range of perspectives.

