The outcomes do not double count any benefits and we only include outcomes that are significant at the 5% level. We request data from the local authorities on the average costs of supporting a child at each level of CSC intervention and use this to determine the "cost (averted)" value. Whilst placement costs vary, we use an average for simplicity. We sum the monetised benefits and disbenefits to arrive at a net benefit.

We do not monetise the other outcomes such as improved behaviour amongst children and young people. This is not to say that these outcomes aren't valuable but simply that there's less agreement on how to put a monetary value on these outcomes. We report a list of outcomes that are significant.

Discounting

Given that all the benefits and costs occur within the same financial year, we do not discount any of the benefits or costs.

Reporting

We report the benefit-cost ratio, and the net present value per child.

Ethics & Participation

An ethics application for this evaluation was submitted to WWCS's research ethics committee on 25th February 2021 with a favourable opinion given on 23rd March 2021.

Consent procedures

Information sheet contents

The information sheets will be tailored to the participant group and will detail the purpose of the project, why they have been invited to take part, what will happen if they take part, whether they have to take part, the possible risks, the possible benefits, the data handling, confidentiality and data protection, the right to withdraw their consent, how the project is funded, what will happen to the results of the project, contact details if they wish to ask further questions.

Social workers

Data collection from social workers will be via an online survey. The first page of the survey will be an information sheet and consent elicitation.

Impact Evaluation: Secondary Data Collection

Children and young people

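### Team-clustered standard errors are fixed for every outcome with no small-sample correction named: in default form a nominal 5% test runs at roughly 9–16% for SDQ if that sample sits mainly in the 14 CLA teams, and at about 7–9% for the surveys

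*Protocol*

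**What the plan says.** The protocol's Analysis plan treats primary and secondary outcomes alike. Under Models: "The dependent variables are continuous and we will use an OLS regression". Under Standard errors it explains that clustering leaves the estimate unbiased but can distort its standard error, and gives as the remedy: "standard errors will be clustered at the level of randomisation, the social worker team level", citing the evaluator's statistical guidance. The regressions are then written out with an error term clustered by team, and Hochberg's step-up procedure is applied across the secondary outcomes. No variance estimator, reference distribution or small-sample correction is named.

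Two groups of secondary outcomes rest on much less than the full sample:

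- **SDQ total difficulties** (Research questions, Secondary outcome 1) is restricted to children "looked after continuously for 12 months or more whose SDQ has been assessed from T4 - T12". Table 1 sorts the 60 teams by type, for example "Looked After Children team (1, 2, 3) (3 CLA teams" in Bexley.
- **Staff and carer self-efficacy and staff stress** come from online surveys, for which the Data collection schedule says "Survey (assume 10% response rate".

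**The concern.** The usual cluster-robust variance is a large-sample formula in the number of clusters. It is too small when few clusters carry the information, when cluster sizes are uneven, or when many covariates give some clusters high leverage. The SDQ analysis probably meets the first two conditions and the survey analyses the third.

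SDQ is the only remaining child outcome measuring behaviour directly, so an over-precise interval there would be prominent. Hochberg's procedure also takes each p-value as valid; if several are too small, its guarantee no longer holds.

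**Working it through.** **The plan's own figures.** The protocol gives no error rate for the clustered test beyond alpha 0.05, two-sided. Its one computed figure is the MDES of 0.127. With 4 authorities × 15 teams × 150 children, ICC 0.03, R² 0.1 (team) and 0.8 (child), df = 4 × (15 − 2) − 3 = 49:

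- variance = 0.03 × 0.9 / (0.25 × 60) + 0.97 × 0.2 / (0.25 × 9000) = 0.00180 + 0.00009 = 0.00189
- MDES = (2.010 + 0.849) × √0.00189 = 0.124

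This is close to 0.127. It concerns the 60-team analysis and has no bearing on SDQ or the surveys.

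**Teams behind SDQ (Table 1).**

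- CLA teams: Bexley 3, Haringey 2, Oxfordshire 7 + 1 = 8, Warwickshire 1; total 14.
- Disability teams: 2 + 2 + 3 + 3 = 10.
- CIN/CPP teams: 4 + 7 + 19 + 6 = 36.

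If only CLA teams contributed, Warwickshire's single team would add no treatment contrast once authority is a fixed effect, leaving 13 informative teams.

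**Survey respondents at 10%.**

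- Table 2: 300 intervention staff, doubled to 600, gives 60.
- Design table: 6–8 × 60 teams = 360–480, gives 36–48.
- Data protection section: about 1,000 staff, gives 100.
- Carers: 424 × 2 × 10% ≈ 85, taking the survey to go to both arms.

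**Parameters in the staff model.** Intercept 1, treatment 1, authority 3, previous measure 1, gender 2, role 2, contract 2, experience 4, team characteristics 5: total 21.

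**Formulas.** With team residual vectors e_g,

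V = (X′X)⁻¹ [Σ_g X_g′ e_g e_g′ X_g] (X′X)⁻¹.

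CR0 uses V as it stands. CR1 multiplies it by G/(G − 1) × (N − 1)/(N − K). CR2 replaces e_g by (I − H_gg)^(−1/2) e_g and takes Satterthwaite degrees of freedom for the treatment coefficient.

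**Simulation under no effect.** The protocol's OLS model was fitted with authority effects, previous measure and listed covariates, under allocation stratified by authority and team type; about 20,000 data sets per setting. Assumed, because the protocol gives no figure: 15 or 40 SDQ children per team, residual ICC 0, 0.03 or 0.13, team-size CV 0 or 0.6, covariate prevalences, and respondents falling at random across teams.

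| Setting | CR1, t(G−1) | CR1, z | CR2, Satterthwaite |
|---|---|---|---|
| SDQ, 14 CLA teams | 8.7–13.1% | 11.4–16.2% | 4.7–6.0% |
| SDQ, 24 teams (CLA + disability) | 7.3–10.4% | 8.7–12.2% | 4.7–5.9% |
| Staff survey, 36 respondents | 7.9–8.5% | 9.2–9.8% | 4.5–4.9% |
| Staff survey, 60 respondents | 6.9–7.9% | 7.8–8.7% | 4.7–5.3% |
| Staff survey, 100 respondents | 7.2–7.4% | 7.9–8.2% | 4.8–5.1% |
| Carer survey, 60–85 respondents | 7.2–7.6% | 7.8–8.6% | 4.9–5.0% |
| All 60 teams, small clusters | 6.5–6.7% | 7.0–7.4% | 5.1–5.3% |

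**Sensitivity to where the SDQ children are.** CR1 with t(G−1), 4,000 data sets per setting, an assumed 40 children per CLA team:

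- CLA plus disability teams averaging 4 children: 12.6% (ICC 0.03) and 14.2% (ICC 0.10).
- All 60 teams, averaging 2 children per CIN/CPP team and 4 per disability team: 12.3% and 13.2%.
- All 60 teams, averaging 10 per non-CLA team: 9.0% at both ICCs.
- Under a different assumed spread, ICC 0.03: CLA plus all Warwickshire teams (23) 7.6%; all 60 teams with uneven sizes 6.5%.

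Teams with only a few children barely raise the effective number of clusters, so the result does not hinge on the count being exactly 14.

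**Source of the survey inflation.** Sixty respondents span about 38 teams. With 200 respondents in about 57 teams, CR1 with t(G−1) still gives 7.2–8.0%. The cause is mainly the many covariates, not a shortage of teams.

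**The case against.** Several stronger readings are tempting, and the protocol does not support them.

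- **That uncorrected errors are prescribed.** They are not. Only the clustering level is fixed; CR2 with Satterthwaite degrees of freedom also satisfies the sentence. The variant may sit in an SAP or in the cited guidance, neither of which is to hand. This stands. But the protocol carries its own detailed analysis plan and presents team clustering as the cure, and the default software form fully complies with it.
- **That SDQ rests on exactly 14 teams, or 24 at most.** No section says so. Warwickshire's only CLA team covers ages 14–18, yet Table 2 gives that authority 148 intervention-group carers, the most of the four. Younger looked-after children there must be held elsewhere. This stands and lowers the inflation, in the mildest setting tried to 6.5%, no worse than the all-60-team analyses.
- **That the surveys suffer from too few clusters.** The effect is modest and comes mainly from the covariates. The 10% response rate sits in the process-evaluation schedule, although the same surveys carry the outcome scales.
- **That the secondary family-wise error rate is shown to be uncontrolled.** No family-wise rate was calculated, and days attended uses administrative data from all teams. What can be said is that Hochberg's guarantee needs valid inputs.
- **That the primary outcome is equally at risk.** With 60 teams the excess is much smaller.

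**Conclusion.** The point holds in limited form. With default cluster-robust errors, a nominal 5% SDQ test would run at roughly 9–16% if the sample sits mainly in the CLA teams, and roughly 7–12% if other teams contribute substantially. Survey outcomes would run at about 7–9% (just under 10% with a normal reference and 36 respondents). Inflation above 5% appeared in every team distribution tried.

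The size rests on an inferred location of the SDQ children, on assumed team sizes and ICCs, and on CR1 being the form used. If the SAP or the cited guidance already requires a small-sample form, the concern is met and the protocol need only say so.

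**What to change.** For SDQ and the staff and carer survey outcomes, state that inference uses CR2 cluster-robust errors by team with Satterthwaite degrees of freedom. Alternatively, use a randomisation test that re-draws the stratified allocation, including the protocol's re-randomisation rule for imbalance. Apply Hochberg to those p-values, and report the number of teams contributing to each outcome. The primary outcome and days attended can keep the present rule, or use the same one for uniformity.

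The change is a sentence or two of wording and standard software. The price is wider intervals: effective degrees of freedom are about 6.5–8.4 for SDQ on 14 teams and about 15 for a staff survey of 60. At 7 df the critical value is 2.36 against 2.16 at 13 df, so intervals widen by 2.36 / 2.16 − 1 ≈ 9% from that source alone, before the larger standard error. That width reflects the information actually available.

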For child outcomes:

$$Y_{ict13} = \beta_0 + \beta_1 D_c + \beta_{2:4} A_c' + \beta_5 Y_{ict0} + \beta_{6:k+6} X_i' + \epsilon_c$$

Where all is defined as above.

Exploratory Analysis

Site effects

In line with WWCS statistical guidance, we account for potential site effects by including a site (local authority) fixed effect and interaction terms between the treatment and sites. The coefficients on these interaction terms can be interpreted as the difference in intervention group mean for that site and the overall treatment mean. The trial is not powered to detect site-specific effects, and so we report only the direction of the site-dosage effects and the standard errors as exploratory analysis. The interpretation of the coefficient on the treatment variable is the simple average between sites (rather than an average weighted by sample size at each site).

Site effects will be tested for all outcomes. The regression specifications will follow the above with the addition of a vector of interaction terms between treatment and local authority fixed effects. E.g. for social workers and foster carer outcomes:

$$Y_{ict13} = \beta_0 + \beta_1 D_c + \beta_{2:4} A_c' + \beta_{5:8} D_c * A_c' + \beta_9 Y_{ict0} + \beta_{9:k+9} X_i' + \beta_{k+9:k+14} M_c' + \epsilon_c$$

Where:

- $D_c * A_c'$ is a vector of interaction terms between treatment and local authority fixed effects.
- And all else is defined as above

Dosage

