- A table of baseline characteristics broken down by treatment arm and response to “pre” data collection and response to “post” data collection (including both those who remained in the sample and those who joined) to check whether characteristics have become more imbalanced by “post” data collection.
- Missing data is likely to be most problematic for data collected via primary data collection (vs routinely collected data). For the outcomes collected via routinely collected data, we will add in an indicator of missingness in the primary data collection and an interaction term between treatment and missingness in the primary data collection. The interaction term can be interpreted as the additional treatment effect on those who are missing from the primary data collection. This gives some proxy as to the likely direction and magnitude of attrition bias for the outcomes collected in the primary data collection.

Reporting

Some of the statistics we will report have been mentioned in earlier sections but we gather them here for ease of reference:

- For each outcome and covariate, we will report the percentage of missing data alongside summary statistics
- Rates of loss to “post” data collection for the arms of the trial
- A table of baseline characteristics broken down by treatment arm and response to “pre” data collection and response to “post” data collection (including both those who remained in the sample and those who joined)
- Description of sites (to allow for qualitative assessment of generalisability of findings)
- ICC at the team level (pre and post for all outcomes)
- Direction and standard errors of the site-treatment effects

Implementation and process evaluation

Aims

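### Reporting only the sign and standard error of the site-by-treatment terms cannot show whether the effect is consistent across the four authorities

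*Protocol*

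**What the plan says.** The Site effects subsection of the protocol's Exploratory Analysis adds interactions between treatment and local authority to the main regression. It concedes that "The trial is not powered to detect site-specific effects" and draws the consequence "so we report only the direction of the site-dosage effects and the standard errors as exploratory analysis". The Reporting list after the missing-data section repeats the rule as "Direction and standard errors of the site-treatment effects".

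The same subsection says what the coefficients mean. Those on the interaction terms "can be interpreted as the difference in intervention group mean for that site and the overall treatment mean". For the main term, "The interpretation of the coefficient on the treatment variable is the simple average between sites", as opposed to an average weighted by site size. The scope is wide: "Site effects will be tested for all outcomes".

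Table 1 gives the team counts by authority: Bexley ("Total: 9 eligible teams"), Haringey ("Total: 11 eligible teams"), Oxfordshire 30 and Warwickshire 10, which makes 60. Nowhere does the protocol promise a site-specific estimate or interval.

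**The concern.** A site analysis in a four-authority trial is there to show whether the effect looks similar across authorities and how precisely that can be judged. The rule drops the estimate and keeps its sign and standard error. Three things follow.

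- A sign does not separate a trivial deviation from a large one.
- A standard error with no estimate cannot be turned into a confidence interval.
- The sign belongs to a deviation from the average, so it is not the sign of that authority's own effect.

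Low power is a reason to show an estimate with its wide interval. It is not a reason to withhold the estimate. At stake is whether the exploratory question can be answered at all from what is published, for every outcome. The main treatment estimate is not at stake.

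**Working it through.** **1. What the signs can show.** I read the interaction terms as the protocol explains them, as deviations of each authority's treatment effect from the simple average. Let the estimated effects be e1 to e4, with mean m = (e1 + e2 + e3 + e4)/4. The terms are d_j = e_j − m, so d1 + d2 + d3 + d4 = 0. Unless all four are exactly zero, at least one is positive and at least one negative. Four matching signs cannot occur, whatever the truth.

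**2. A negative sign with a positive effect.** Take three authorities at 0.127 SD and one at half that, 0.0635 SD (illustrative values). Then m = (3 × 0.127 + 0.0635)/4 = 0.111. The fourth authority's term is 0.0635 − 0.111 = −0.048. It would be reported as negative although its effect is positive.

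**3. The plan's own precision.** Inputs from Sample size / MDES calculations: ICC 0.03, child-level R² 0.8, team-level R² 0.1 with 3 covariates, 150 children per team, 60 teams, half treated, two-sided alpha 0.05, power 0.8.

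- Variance = 0.03 × 0.9/(0.25 × 60) + 0.97 × 0.2/(0.25 × 60 × 150) = 0.001800 + 0.000086 = 0.001886, so SE = 0.0434.
- Degrees of freedom = 4 × (15 − 2) − 3 = 49; multiplier 2.859.
- MDES = 2.859 × 0.0434 = 0.124, against the stated 0.127 (2.2% lower). That is close enough to use the inputs.

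**4. Precision by authority.** With the same variance and each authority's own number of teams J, SE = √[(0.03 × 0.9 + 0.97 × 0.2/150)/(0.25 J)] = √(0.1132/J). The SE of a deviation is √[(9/16) SE_j² + (1/16) Σ SE_k²], summing over the other three. Half-widths use t on J − 2 degrees of freedom.

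| Authority | Teams | SE of own effect | 95% CI half-width | SE of deviation |
|---|---|---|---|---|
| Bexley | 9 | 0.112 | 0.27 | 0.093 |
| Haringey | 11 | 0.101 | 0.23 | 0.087 |
| Oxfordshire | 30 | 0.061 | 0.13 | 0.065 |
| Warwickshire | 10 | 0.106 | 0.25 | 0.090 |

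These SEs are indicative only, because the protocol justifies the 0.8 by how well baseline predicts endline SDQ, and the primary outcome is now the sum of escalations and de-escalations. Setting the child-level R² to 0 gives own-effect SEs of 0.122, 0.110, 0.067 and 0.116, a modest change. Nothing comparable is given for the staff and carer outcomes.

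**5. The reported signs under these inputs.** With identical true effects in all four authorities (400,000 draws), the signs split 2–2 in 64% and 1–3 in 36%, with all alike in 0%. If true effects do differ, with an assumed between-authority SD of 0.05, the sign of a given deviation is wrong in 31–36% of draws. With an assumed SD of 0.10 it is wrong in 21–26%. The protocol gives no expected heterogeneity, so both SDs are assumptions.

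**The case against.** The protocol is open about the limits. It calls the analysis exploratory and unpowered, explains the coefficients, and publishes standard errors that show the imprecision. It also plans a description of sites and a focus group in each authority. The full estimates can be printed when the report is written. All of this stands and keeps the point small, but none of it makes a sign and a standard error interpretable. The statement that site effects will be tested does not rescue the rule either. A p-value would let a reader work back to the estimate, but the rule limits reporting to direction and standard error.

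Three stronger readings are tempting, and the document does not support them.

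- *The signs are largely noise in every authority, with a stated chance that an authority's effect points the wrong way.* If the true effect were 0.127 SD everywhere, the chance that an authority's own estimate has the wrong sign is about 13% (Bexley), 11% (Haringey), 2% (Oxfordshire) and 12% (Warwickshire), and 32% for at least one. Those figures describe own effects, whereas the plan reports signs of deviations. They also mean a correct sign 87–98% of the time, and Oxfordshire holds half the teams.
- *The plan omits a joint test of heterogeneity.* That is detail a statistical analysis plan may hold, and only the protocol is at hand.
- *The report will mislead the authorities.* How readers would take a plus or minus is conjecture.

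One technical reservation remains. The printed equation has three authority coefficients (2 to 4) but four interaction coefficients (5 to 8), so the coding is not fully settled. With reference-category coding the signs need not be mixed. They would then be relative to one chosen authority, and the main coefficient would be that authority's effect, which conflicts with the stated interpretation. In neither case is the sign that of the authority's own effect.

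**Conclusion.** The point holds as a minor reporting weakness. Under the protocol's own definition of the terms, mixed signs are guaranteed, so direction carries no information about consistency, and the standard errors alone give no interval. This conclusion is algebraic. It rests on the stated interpretation of the coefficients and not on the power inputs. The numerical precision in the table does rest on SDQ-based inputs and is only a guide to how wide the intervals would be. Randomisation, the primary estimate and its standard error are untouched.

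**What to change.** In the Site effects subsection and in the Reporting list, replace the direction-and-standard-error rule with each authority's treatment effect (main term plus its interaction term) and a 95% confidence interval based on team-clustered standard errors. Label the results exploratory and state that signs alone are not interpreted. An authority's total effect does not depend on how the interaction is coded, so this also removes the ambiguity in the equation. Align the wording of the two places, since one speaks of site-dosage effects and the other of site-treatment effects. A single joint test of the interaction terms (3 degrees of freedom) is an optional addition.

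The estimates come from the model already planned, as linear combinations of its coefficients. The cost is one extra table or plot per outcome, plus a caveat because the wide intervals could themselves be over-read.
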